### **8.3 Data Analysis Plans**

For the Phase I primary objective, we will summarize the toxicities of the patients. For the Phase II primary objective of estimating the rate of resolution of the malignant pleural effusion re-accumulation following IV nivolumab combined with intrapleural injection of talimogene laherparepvec, the percent of patients will be reported with a 95% confidence interval, and compared to the null using a chi-squared test.

Response rates and adverse events will be reported. Progression free survival, overall survival, and time to symptomatic pleural re-accumulation will be estimated using the Kaplan-Meier method. Available quality of life data will be summarized over the course of the study.

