Clinically, nearly 50% of patients with metastatic malignancies develop a malignant pleural effusion. More than 80% of these cases are represented by cancers of the lung, breast, gastrointestinal system, ovaries or lymphoma. While malignant mesothelioma is the most common type of primary pleural tumor, lung and breast cancer are the most common malignancies found to be associated with MPE in male and female patients, respectively [1, 14, 15].

The diagnosis of MPE implies advanced disease with median survival of four months, with lung cancer associated with the shortest survival [16]. Currently treatment for MPE centers on palliation of associated symptoms, most commonly

[figure not shown]
dyspnea and respiratory distress. Palliation of symptomatic malignant pleural effusion consists of serial thoracentesis, chemical pleurodesis and tunneled pleural catheter placement. At this time there are clinical trials aimed at decreasing fluid formation including combination intrapleural bevacizumab (anti-VEGF) and cisplatin therapy for MPE from NSCLC (NCT01661790). These efforts highlight the need for novel approaches to the treatment of MPE.

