### 2.4.2 Secondary Endpoints

**2.4.2.1 Median PFS.** PFS will be defined as the time from D1 of treatment until death or progression.

**2.4.2.2 Median OS.** OS is defined as the time from D1 of treatment to death from any cause.

**2.4.2.3 Tumor response** will be defined as the proportion of patients with reduction in tumor (irCR+irPR) per irRECIST criteria outlined in section 6.8.

**2.4.2.4 Clinician assessed toxicity** will be classified and graded according to the National Cancer Institute's Common Terminology Criteria for Adverse Events (NCI-CTCAE, version 5.0).

**2.4.2.5 Use of modified Borg rating scale** for perceived dyspnea (10 point scale from 1 to 10 which measures perception of dyspnea) [59, 60] (Provided in 11.6 **Appendix F: Borg Scale**).

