In Dose Level 2 (expected Phase II dose), the first 3 patients will receive both IP talimogene laherparepvec and IV nivolumab. The first dose of talimogene laherparepvec will be administered on Cycle 1, Day 1 at 4mL of  $10^6$  pfu/mL in 200 cc normal saline (IP) to seroconvert HSV-seronegative patients. Three weeks will be given for seroconversion. Subsequent doses of talimogene laherparepvec at 4ml of  $10^8$  pfu/mL + Nivolumab 240 mg IV will be administered every two weeks starting on Cycle 2, Day 1 for up to 8 cycles of therapy. Patients will be assessed for DLTs related to IP administration of talimogene laherparepvec after seroconversion and 2 cycles of combination therapy (i.e., 7 weeks of study treatment). If  $\geq 2$  patients experience DLT, the study will be discontinued. If 1 patient out of 3 has DLT, 3 additional patients will be recruited and treated at the same dose level. If 0 out of 3 or  $\leq 1$  patient out of 6 has a DLT in the dose level 2 cohort, the study will recruit additional patients in Phase II at this dose level and accrue a total of 24 patients as per study goal. All patients treated at dose level 2 in Phase I or Phase II, will be included in analyses of safety and efficacy. Safety stopping rules will ensure the safety of subjects receiving combination treatment in Phase II (see [Statistical Considerations in section 9.0.](#))

Subjects may continue talimogene laherparepvec for up to 9 cycles (i.e. alone or with nivolumab) until resolution of pleural effusion or they experience systemic disease progression. Subjects who have resolution of pleural effusion as defined by

the primary endpoints may continue nivolumab monotherapy per standard of care until disease progression (see section 4.2 for details on treatment and section 6.5.2).

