## Key to Time and Events Table Footnotes

1. Radiological assessments, EKG and physical exam may be performed up to 4 weeks prior to day 1 of treatment. Other evaluations except for pregnancy must be performed within 2 weeks prior to Cycle 1 Day 1 of treatment. Serum B-HCG must be performed within 72 hours prior to first dose of study medication for women of child-bearing potential. Screening labs performed within 72 hours prior to Cycle 1 Day 1 do not need to be repeated on C1D1.
2. The first treatment cycle with talimogene laherparepvec is 3 weeks in length (21 days) to allow for seroconversion (See Schema in 4.1). Subsequent treatment cycles are to be repeated every 2 weeks (14 days) X 8 cycles or until progression, whichever occurs first. **A window of +/- 2 days applies to all study visits within the treatment period.**
3. **Visit may be deemed optional at the behest of the investigator.**
4. The end of treatment/safety follow up visit should only occur when patients permanently stop study treatment and should be performed 30 days (+/-7 days) after the last dose of study medication. Patients who have an ongoing  $\geq$ grade 2 or serious AE (SAE) at this visit will continue to be followed until the event is resolved or deemed irreversible by the investigator. Patients stopping nivolumab should be monitored for at least 100 days after discontinuing the drug for the emergence of SAEs. After two years of follow-up per standard of care (**Q3 months +/- 15 days**) as outlined in the time and events table, subsequent follow up will be by phone contact or via medical records to document disease progression and survival information until death (Q3 months +/- 15 days).
5. Complete history at baseline only (to include smoking history); thereafter focused history on symptoms/toxicity physical exam to include height (baseline only), examination of the skin, weight, pulse oximetry, and vital signs.
6. Tumor imaging should remain consistent throughout study, and should include those thought by investigator to best capture status of disease. Examples include PET, contrasted computed tomography (CT) of the chest, abdomen and pelvis, and bone scan. During the treatment period scans should occur prior to Cycle 5 Day 1 and every 4 cycles after that until progression. Imaging following completion of study procedures should be per standard of care for the relevant disease state.

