7. Hematology: CBC with differential and platelet count; Liver function tests: total bilirubin, AST (SGOT), ALT (SGPT), and alkaline phosphatase; direct bilirubin if indicated, at screening only. Serum chemistry: potassium, sodium, calcium, creatinine, chloride, glucose, magnesium, phosphorus, BUN, albumin, uric acid, and total protein.
8. Coagulation: PT or INR and PTT or aPTT
9. Talimogene Laherparepvec administration only through Cycle 9.
10. Patient drainage diary (See Appendix E in Section 11.5)
11. Collect urine, pleura and 5 mL of blood (lavender top EDTA tube) at each time point denoted below. Additional details on sample collection provided in the study laboratory manual
  - C1D1: predose, 1 hr post dose, 4 hrs post dose and 6 hrs post dose samples
  - Collect predose samples on C1D8/C2D1/C2D8/C3D1/C4D1 and at end of treatment
12. Blood samples will be collected for correlative studies (3x 8mLs whole blood in ACD tubes will be collected to evaluate for clonally restricted circulating B and T cells).

13. Tumor biopsy will be collected for correlative studies. All subjects in this study will have had pleural catheter placed as standard of care, which will allow for fresh biopsy collection. If for some reason fresh biopsy cannot be collected, archival tumor will be accepted.
14. Pleural fluid will be collected studies at the following time points: pre treatment, 3 weeks post treatment, 9 weeks post treatment, and end of treatment, separated by the LCCC Immune Monitoring and Genomics Facility (IMGF) into two portions: one portion (prioritized) will be used for correlative studies and the second portion will be distributed to CTU lab for long term storage.
15. Modified Borg Rating of Perceived Dyspnea (MBS) will be used to assess level of exertion (**Provided in 11.6 Appendix F: Borg Scale**).
16. Buccal swab for matched normal genomic DNA
17. Repeat if insufficient sequencing.

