#### 6.4.6 Day 1/Cycle 5-N Safety Run-in/Phase II expansion (6.1, 6.2)

Physical examination (including weight and pulse oximetry)

ECOG Performance Status (see appendix A)

Laboratory evaluations (to be obtained prior to treatment):

- CBC with differential
- Serum chemistries (potassium, sodium, calcium, creatinine, chloride, glucose, magnesium, phosphorus, BUN, albumin, uric acid, and total protein)
- Liver function tests (total bilirubin, direct bilirubin, alkaline phosphatase, AST, ALT)

Concomitant medication(s): All concomitant medications will be recorded.

Toxicity evaluation: Use NCI CTCAEv5.0

Tumor evaluation: CT or MRI scan of the neck, results from physical examination head and neck, and chest imaging (x-ray or CT scan at discretion of physician).

Scans are to be performed prior to Cycle 5 Day 1 and every 4 cycles after until disease progression.

For Safety run-in cohort 1 (6.1): Administer talimogene laherparepvec only  $4 \times 10^8$  pfu via pleurX catheter per standard of care of related disease state

For Safety run-in cohort 2 and Phase II expansion (6.2): Administer talimogene laherparepvec  $4 \times 10^8$  pfu via pleurX catheter + 240 mg nivolumab IV

Patient diaries

Chest x-ray as needed and/or after three consecutive drainages with  $\leq 50$ cc drainage (every other day drainages) of pleural fluid drainage accompanied by patient-defined improvement in symptoms (cough, chest pain and/or dyspnea).

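### Section 8.3 applies Kaplan-Meier to time to symptomatic pleural re-accumulation, a non-fatal outcome not listed in section 2, and gives no rule for deaths

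*Combined protocol and SAP*

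**What the plan says.** The last paragraph of section 8.3 puts three time-to-event outcomes under one method: "Progression free survival, overall survival, and time to symptomatic pleural re-accumulation will be estimated using the Kaplan-Meier method".

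The first two are defined in section 2.4.2. For progression, "PFS will be defined as the time from D1 of treatment until death or progression". OS runs from the same day to death from any cause. Both therefore have an origin, and death is an event in both.

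The third outcome is not among the objectives in 2.1 to 2.3 or the endpoints in 2.4. Those list resolution, toxicity, PFS, OS, irRECIST response, the Borg scale and the correlative work. Section 8.3 does not say what counts as a symptomatic re-accumulation, when the clock starts, whether all treated patients or only those whose effusion resolved are at risk, or what happens to a patient who dies first. No competing-risk method is mentioned.

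Death is a realistic competing event. Section 1.2 says: "The diagnosis of MPE implies advanced disease with median survival of four months".

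The length of pleural observation depends on treatment. Under 4.1.1, subjects with resolution as defined by "the primary endpoints may continue nivolumab monotherapy per standard of care until disease progression". Footnote 9 to the 6.2 table reads "Talimogene Laherparepvec administration only through Cycle 9", and footnote 4 says "The end of treatment/safety follow up visit should only occur when patients permanently stop study treatment", 30 days (±7) after the last dose. Section 6.5.2 limits visits after study therapy to later cancer treatment, related SAEs and survival. The 6.2 table nevertheless marks toxicity assessment and tumor measurement at long-term follow-up.

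**The concern.** Kaplan-Meier turns into a probability cleanly when every patient could still have the event after the last time observed. That holds for PFS and OS, where death is part of the event. A patient who dies without re-accumulation can no longer have one. If that death is treated as censoring, the estimator in effect assumes the patient would have gone on to re-accumulate at the same rate as the survivors. One minus Kaplan-Meier (1−KM) then describes a setting in which nobody dies. It can never be below the proportion who actually re-accumulate, and it lies above that proportion once a death comes before a re-accumulation.

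If death is counted as an event instead, Kaplan-Meier is valid, but the curve shows re-accumulation or death and should be labelled so.

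The sentence in 8.3 therefore supports two different curves, and nothing in the plan fixes the choice before the data are seen. What is at stake is how one descriptive result is read, not a decision of the trial.

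**Working it through.** **Plan's own figures.** The documents give no figure for re-accumulation. The one stated efficacy design figure is the primary test in 8.2: 45% against 70%, two-sided 0.10, 80% power, 24 patients. The one-group chi-squared approximation gives n = 23.2, rounded up to 24, with approximate power 81.2% at 24. It reproduces, and nothing below touches it.

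**Inputs, all assumed.** Constant, independent hazards. Re-accumulation median R = 6 months, for which the documents give no rate. Survival median S = 4, 8 or 12 months: four is the general background figure in 1.2, and the other two allow for fitter patients (ECOG ≤ 2).

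**Formulas.** With a = ln2/R and b = ln2/S per month:
- deaths censored: 1−KM = 1 − exp(−aT)
- cumulative incidence: CIF = a/(a+b) × [1 − exp(−(a+b)T)]
- composite with death: 1 − exp(−(a+b)T)

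Example, S = 4 and T = 2: a = 0.1155, b = 0.1733, so 1−KM = 20.6%, CIF = 0.4 × 43.9% = 17.6%, and the composite is 43.9%.

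| Months | 1−KM | CIF (S = 4, 8, 12) | Overstatement, points | Composite |
|---|---|---|---|---|
| 2 | 20.6% | 17.6, 19.0, 19.5% | 3.1, 1.6, 1.1 | 43.9, 33.3, 29.3% |
| 4 | 37.0% | 27.4, 31.7, 33.3% | 9.6, 5.3, 3.7 | 68.5, 55.5, 50.0% |
| 6 | 50.0% | 32.9, 40.2, 43.1% | 17.1, 9.8, 6.9 | 82.3, 70.3, 64.6% |

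Over R = 3 to 12 and S = 4 to 12, the overstatement is 0.6 to 5.3 points at 2 months, 2.1 to 14.5 at 4 and 4.3 to 22.9 at 6.

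**Against sampling noise.** Simulation used 40,000 runs with 15 patients at risk and no other censoring. Fifteen is the rejection cut-off in 8.2, taken here as an illustrative number of resolvers. At R = 6 the SD of 1−KM is 11 to 12 points at 2 months, 13 to 16 at 4 and 14 to 19 at 6, so the bias stays below one SD. That does not hold for every input: at R = 3, S = 4 and 6 months it is 22.9 points against an SD of about 16, or about 1.4 SD. The Kaplan-Meier figure was below the Aalen-Johansen figure in none of the R = 6 runs.

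**Which times can be observed.** Cycle 2 Day 1 is 21 days after D1, and Cycle 9 Day 1 is 21 + 7 × 14 = 119 days. Adding 30 days for the end-of-treatment visit gives 149 days, or 4.9 months. Suppose the clock starts at resolution and the patient does not continue nivolumab beyond Cycle 9. Four months (about 122 days) of observation then requires resolution by about day 149 − 122 = 27, days after Cycle 2 Day 1. Six months is impossible. Two months (about 61 days) requires resolution by about day 88. The 4- and 6-month rows thus apply mainly to resolvers who stay on nivolumab longer.

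**The case against.** The strongest reply is that the bias is inferred rather than found in the plan. Section 8.3 does not say that deaths are censored. Its two companion outcomes both count death, so a composite reading is open, and Kaplan-Meier would then be valid. Nor does 8.3 promise a 1−KM percentage or a landmark time. This stands, and it is why the point is conditional. A reader might infer that the plan commits to a biased estimator; the text does not support that. What it supports is that the rule is missing and that the two readings give different curves: at R = 6 the composite exceeds 1−KM by 8.7 to 23.3 points at 2 months (29.3 − 20.6 and 43.9 − 20.6).

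The second reply is that the magnitudes rest on assumptions. This also stands. A reader might take four months as this trial's survival and quote 17 points as the expected error. Section 1.2 gives four months only as background for malignant effusion in general, no re-accumulation rate is given, and many patients will not be observed that long.

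The third reply is that no decision depends on the outcome, and that deleting the clause would also close the gap. Both are true. They limit the weight of the point but do not remove it while the analysis stays in the plan.

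**Conclusion.** The point holds as a minor one. Section 8.3 assigns Kaplan-Meier to a non-fatal outcome that section 2 does not list, without the definitions needed to know what the curve estimates. The omission is certain. The bias follows only if deaths are censored and 1−KM is read as the probability of re-accumulation. It then runs upward, against the treatment.

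At the assumed inputs (R = 6; S = 4 to 12) the overstatement is 1.1 to 3.1 points at 2 months, the time most relevant to patients who stop by Cycle 9. The larger figures, 3.7 to 9.6 points at 4 months and 6.9 to 17.1 at 6, matter mainly for resolvers who continue nivolumab. With 15 patients these are below one SD of the estimate; with re-accumulation twice as fast, the bias can exceed one SD.

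It would be wrong to infer any effect on the primary conclusion. Resolution is analysed as a proportion, and the 15/24 rule, the chi-squared test and the sample size do not use this outcome.

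**What to change.** In 8.3, keep Kaplan-Meier for PFS and OS. For re-accumulation, choose one of the following before the data are examined:

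- **Cumulative incidence (Aalen-Johansen)**, with death without re-accumulation as the competing event. State the event and its data source, the origin and the at-risk set. Censor living patients at their last pleural assessment. Count deaths only within the period in which pleural status is collected, and show numbers at risk. That period must first be settled by reconciling the long-term follow-up marks in the 6.2 table and its footnote 4 with the narrower content in 6.5.2. Otherwise deaths would be counted over a longer period than re-accumulations.
- **Re-accumulation-free survival**, with death as an event, keeping Kaplan-Meier and using that name. The event, origin and at-risk set still need stating.

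Either way, list the endpoint in 2.4.2.

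The cost is a few sentences in 8.3, one line in 2.4.2 and a standard software routine, with no added visits. The drawback of cumulative incidence is that observation length differs between patients, so few may be at risk at later times. The drawback of the composite is that it no longer isolates re-accumulation.

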## 6.2 Safety Run-in Cohort 2 and expansion (Combination)

Assessments	Pre-Study 	Treatment Period 							Follow up	
		Cycle 1 is 3 weeks in length, subsequent cycles are Q2W							End of TXT 	Long Term FU 
		Cycle 1 Day 1 	Cycle 1 Day 8	Cycle 2 Day 1	Cycle 2 Day 8 	Cycle 3 Day 1	Cycle 4 Day 1	C5 – 9N Day 1		
Informed Consent	X									
HSV-1 antibody	X									
History 	X									
Physical exam 	X	X	X	X	X	X	X	X	X	
Performance Status	X	X	X	X	X	X	X	X	X	
EKG	X						X			
Troponin	X						X			
Chest x-ray	X	As needed and within 21 days of final drainage ≤ 50 mL							X	
Tumor measurement 	X							X 	X 	X
Pregnancy test 	X									
Hematology 	X	X	X	X	X	X	X	X	X	
Serum chemistries 	X	X	X	X	X	X	X	X	X	
Liver function tests 	X	X	X	X	X	X	X	X	X	
Coagulation 	X									
Toxicity Assessment	X	X	X	X	X	X	X	X	X	X
Concomitant Meds	X	X	X	X	X	X	X	X	X	
talimogene laherparepvec IP Q3W 10  PFU		X								
talimogene laherparepvec IP Q2W 10  PFU 				X		X	X	X		
Nivolumab IV Q2W		X		X		X	X	X		
Patient diary 		X	X	X	X	X	X	X	X	

Assesments	Pre-Study 	Treatment Period  Cycle 1 is 3 weeks in length, subsequent cycles are Q2W							Follow up	
		Cycle 1 Day 1 	Cycle 1 Day 8	Cycle 2 Day 1	Cycle 2 Day 8 	Cycle 3 Day 1	Cycle 4 Day 1	C5 – 9N Day 1	End of TXT 	Long Term FU 
Blood/urine/pleura samples to assess viral shedding		X 	X 	X 	X 	X 	X 		X 	
Blood sample for correlative studies 		X		X			X		X	
Tumor biopsy 	X									
Collection of pleural drainage 		X		X			X		X	
Buccal Swab	X 	X 								
Modified Borg 		X		X			X		X	
Survival analysis										X

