#### 6.5.2 Subsequent Follow-up

Subjects withdrawn from study therapy will be followed every 3 months (+/- 15 days) per standard of care. These visits will be limited to history of any subsequent cancer treatments, an assessment of any SAE's considered to be possibly or probably related to study treatment until resolution, and survival status. After two years of follow-up as described in the time and events tables, subsequent follow-up will be per standard of care and subjects will be contacted by phone or via medical records for progression and survival information (every 3 months +/- 15 days) until death.

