#### **Instructions to All Patients:**

Keep track of each of your PleuRx® catheter drainages using the attached PleuRx® Catheter Diary. Complete all of the information in this diary unless the information does not apply to you, in which case you should enter N/A for Not Applicable. For the pain question, please enter a number from 0 to 10 describing any pain you had from your catheter drainage, where 0 equals No Pain and 10 equals the Worst Possible Pain. If you took any medicines for pain you had from your catheter drainage, please tell us what medicines you took and how much of those medicines you took in the Pain Med Details section. Finally, please tell us if you had any problems or complications from your catheter drainage and describe them in the Problem Details section. If you have any questions about your catheter drainage or completion of this diary, please talk with your physician.

If you drain <50ml of fluid from your PleuRx® catheter for three consecutive drainages, please call your doctor to see if the catheter needs to be flushed or removed.

Contact numbers:

[name]: [contact] (office)

[name]: [contact] (office)

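### Section 8.3 plans a time to symptomatic pleural re-accumulation, but no scheduled effusion assessment follows the end-of-treatment visit and no origin, event or censoring rule is given

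*Combined protocol and SAP*

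**What the plan says.** Section 8.3 states that "time to symptomatic pleural re-accumulation will be estimated using the Kaplan-Meier method", alongside PFS and OS. It does not say when the clock starts, what counts as the event, or when an event-free patient is censored. The endpoint does not appear among the secondary objectives (2.2) or the secondary endpoints (2.4.2).

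Table 6.2 covers the combination cohort and the Phase II expansion, which form the efficacy population. Its diary, chest x-ray and modified Borg rows all have a last entry under end of treatment and a blank under long-term follow-up. The on-treatment chest x-ray entry reads "As needed and within 21 days of final drainage ≤ 50 mL". Table 6.1 is the same for the long-term column of these three rows.

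On the timing of the last assessment, the table footnotes say "The end of treatment/safety follow up visit should only occur when patients permanently stop study treatment", and place it 30 ± 7 days after the last dose.

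Section 6.5.2 then says of the 3-monthly visits: "These visits will be limited to history of any subsequent cancer treatments", together with SAEs possibly or probably related to treatment and survival status. After two years, patients are "contacted by phone or via medical records for progression and survival information". The effusion is not mentioned in either period.

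**The concern.** The primary endpoint is met by three consecutive low every-other-day drainages with symptom improvement. It does not show whether resolution lasts. The Kaplan-Meier estimate in section 8.3 is the only planned measure of durability, and the schedule stops collecting the data it needs about a month after the last dose.

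The length of effusion observation is also set by time on drug. A resolved patient may continue nivolumab until progression (4.1.1, 4.2) and keeps the diary and as-needed x-ray during that time. A patient who stops loses them at the end-of-treatment visit. Progression is one of the listed reasons for stopping (4.5), so observation of the effusion may end when recurrence becomes more likely.

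**Working it through.** The plan gives no figure for this endpoint, so there is none to reproduce. The check has three parts.

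**1. What is collected after end of treatment (Table 6.2 and text)**

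| Source | After end of treatment | Captures symptomatic re-accumulation? |
|---|---|---|
| Diary, chest x-ray, Borg | None | No |
| 3-monthly visit (6.5.2) | Later treatment, related SAEs, survival | Only as a related SAE |
| Toxicity row, long-term column | Marked, but 6.5.2 narrows it to related SAEs | Incidentally |
| Non-serious AEs | To 100 days after nivolumab (7.2); 30 days in 7.1.1, which also excludes progression unless attributed to therapy | Incidentally |
| SAEs (7.3.1) | At least 100 days | Incidentally |
| Tumour imaging | Standard of care, no fixed schedule, no symptom question | Incidentally |
| History row | Long-term column marked in Table 6.1 only | Not in the efficacy population |

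Calendar: doses fall on days 1 and 22 and then every 14 days, so the ninth is on day 22 + 7 × 14 = 120. The end-of-treatment visit is then about day 120 + 30 = 150. If the last dose is cycle 3 (day 36), it is about day 66. Patients continuing nivolumab have it later.

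**2. Effect of the censoring rule when stopping is unrelated to recurrence**

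Assumptions, none from the documents: time runs from resolution; recurrence is exponential with median m = 3, 6 or 12 months; the effusion is observed for W = 1, 2 or 4 months after resolution; median survival is 8 months from resolution; follow-up is 24 months.

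- *Censor at the last effusion assessment.* The estimate follows 2^(−t/m) up to W and does not exist beyond it. Simulation (200,000 subjects, m = 6, W = 4) gives 0.654 at 3.7 months against a true 2^(−3.7/6) = 0.652. The curve is short but not inflated.
- *Carry event-free to death or last contact.* No event can occur after W, so the curve stays flat at 2^(−W/m). The truth at 6 months is 2^(−6/m).

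| m (months) | True at 6 months | W = 1 | W = 2 | W = 4 |
|---|---|---|---|---|
| 3 | 0.25 | 0.79 | 0.63 | 0.40 |
| 6 | 0.50 | 0.89 | 0.79 | 0.63 |
| 12 | 0.71 | 0.94 | 0.89 | 0.79 |

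Simulated values agree to within rounding.

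The share of recurrences (before death or 24 months) that fall after W is 1 − (1 − e^(−(λ+μ)W)) / (1 − e^(−(λ+μ)24)), with λ = ln 2/m and μ = ln 2/8. For m = 6 and W = 4, λ + μ = 0.1155 + 0.0866 = 0.202, so the share is 1 − 0.555/0.992 = 0.44. Over the grid it runs from 28% to 86%.

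**3. Effect when recurrence risk may change after stopping**

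Assumptions: re-accumulation 0.05 per month on therapy; death 0.17 per month (median ln 2/0.17 = 4.1 months, close to the four months in section 1.2); end of treatment one month after stopping. The stopping and post-stop rates vary as shown. Entries are the 6-month re-accumulation probability, 1 − KM, from simulation with 300,000 subjects per row; a repeat run agreed within 0.003.

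| Stop rate/month | Post-stop re-accumulation/month | Full ascertainment | Censored at end of treatment | Carried to last contact | 6-month recurrences after that visit |
|---|---|---|---|---|---|
| 0.2 | 0.05 | 0.258 | 0.260 | 0.184 | 23% |
| 0.2 | 0.10 | 0.343 | 0.295 | 0.212 | 31% |
| 0.2 | 0.20 | 0.464 | 0.356 | 0.264 | 37% |
| 0.4 | 0.20 | 0.560 | 0.427 | 0.250 | 47% |

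In the first row the risk does not change on stopping, and censoring at end of treatment gives the right answer. Bias under that rule appears only where the risk is assumed to rise after stopping. Carrying patients forward understates recurrence in every row.

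**The case against.** The strongest reply has four parts.

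- **The schedule alone does not inflate the curve.** A reader might infer that durability will look too good whatever the analyst does. The documents do not support that. Section 8.3 does not say that patients are carried event-free to last contact, and censoring at end of treatment is unbiased when stopping is unrelated to recurrence risk (0.258 against 0.260). Nothing in the documents shows that the risk rises on stopping. This stands, and it limits the claim.
- **Some recurrences would still be recorded.** The AE and SAE windows, standard-of-care imaging, and the rule in 7.3.3.5 that significant worsening on x-ray or examination be recorded are all real routes. They are not systematic, however. Imaging carries no symptom question, and 7.1.1 lets a recurrence judged to be progression go unrecorded. The simulations give these routes no credit, so the shares missed are upper values under their assumptions.
- **Observation can run past progression.** Section 4.5 allows treatment until a confirming scan about 6 weeks later, and the end-of-treatment visit follows 30 days after the last dose: about 42 + 30 = 72 days for patients so continued. This weakens the link between progression and loss of observation but does not remove it.
- **The analysis is minor.** It is a descriptive line in a 24-patient single-arm trial, with no test or decision attached, and it is absent from 2.2 and 2.4.2. This stands as a limit on importance. It does not explain why the plan would estimate a quantity whose later events it does not collect.

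**Conclusion.** The mismatch is real. Section 8.3 plans a durability estimate, and the schedule ends effusion assessment 30 ± 7 days after the last dose without any effusion item in later follow-up. The consequence depends on a censoring rule that is not stated:

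- Censored at the last effusion assessment, the estimate says nothing beyond that point. It is also biased if stopping treatment is linked to recurrence risk, which is plausible because progression ends treatment but is not shown.
- Carried event-free to last contact, it is too favourable.

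The sizes above are illustrative. The re-accumulation and stopping rates, the observation windows and the choice of resolution as time origin are all assumptions; only the death rate in the third part is tied to a figure in the protocol. They show that the choice of rule matters, not how large the error will be in this trial. The primary resolution rate, its 15-of-24 rejection rule and the sample size are untouched.

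**What to change.** **Data.** Add to section 6.5.2, and to the long-term follow-up column of Tables 6.1 and 6.2, one dated item collected at the existing 3-monthly contact or from the chart: symptomatic recurrence of the effusion, or any repeat pleural procedure.

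**Analysis.** In section 8.3, define:

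- the time origin as the date of resolution, so that the estimate applies to patients who resolved;
- the event from the on-treatment assessments plus the new item;
- censoring at the last contact at which effusion status was recorded, not at the last survival contact.

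**Cost.** One extra CRF item, with no added visit or imaging and no change to the primary analysis. Recurrence dates after end of treatment would be recalled by the patient or taken from the chart at 3-monthly intervals, so they will be less exact than those from the diary. The item should be added before patients reach follow-up, because dates may be hard to recover later, particularly after death.
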